13.2. Definition of serious adverse event (SAE)

An AE or suspected adverse reaction is considered "serious" if, in the view of either the investigator or sponsor, it results in any of the following outcomes: death, a life-threatening adverse event, inpatient hospitalization or prolongation of existing hospitalization, a persistent or significant incapacity or substantial disruption of the ability to conduct normal life functions, or a congenital anomaly/birth defect. Important medical events that may not result in death, be life-threatening, or require hospitalization may be considered serious when, based upon appropriate medical judgment, they may jeopardize the patient or subject and may require medical or surgical intervention to prevent one of the outcomes listed in this definition.

13.3. AE and SAE collection and reporting

13.3.1. AE and SAE collection. Adverse event information will be collected at every planned and unplanned in-person and telephone visit until 7 (for non-serious AEs) or 30 days (for SAEs) after the last day of study participation. At each study visit, the investigator will inquire about the occurrence of AE/SAEs since the last visit. Events will be documented using an AE log eCRF (EDC entry) and followed for outcome information until resolution or stabilization.

13.3.2. AE and SAE reporting. All AEs will be recorded in the eCRF. SAEs must be reported on a SAE report form and on the AE pages in the eCRF. All SAEs must be reported immediately by the site investigator, within one calendar day (24 hours) from time of awareness by email to the Project Director and the ADCS.

All safety related information will be collected and processed promptly, to comply with regulatory requirements. An adverse event or suspected adverse reaction is considered "unexpected" if specificity or severity exceeds what that has been observed in previous studies. "Unexpected," as used in this definition, also refers to adverse events or suspected adverse reactions that are mentioned in the investigator brochure as occurring with a class of drugs or as anticipated from the pharmacological properties of the drug, but are not specifically mentioned as occurring with the particular drug under investigation.

Suspected Unexpected Serious Adverse Events (SUSARs) will be reported to the FDA and IRB in an expedited manner as follows: fatal or life-threatening SUSARs – as soon as possible but no later than 7 calendar days after the sponsor's initial receipt of the information: non-fatal and non-life threatening SUSARs—as soon as possible but no later than 15 calendar days after the sponsor determines that the information qualifies for reporting. Relevant follow-up information for fatal or life-threatening SUSARs will be provided to the FDA and IRB.

The UC Irvine regulatory team will report events meeting reporting criteria to the UCI IRB (IRB of record) within 5 business days. Once the SAE is reported, the ADCS DSMB liaison will communicate the information to the DSMB. In the event that the Project Director, ADCS, DSMB, or the IRB determine that the safety information related to the study has changed, site investigators and the remaining parties will be notified as soon as possible, but in no case later than 15 calendar days from said determination.

13.3.3. Data Safety Monitoring Board (DSMB). This trial will utilize the ADCS DSMB. The DSMB will be provided with regular safety reports approximately every 3 months (see DSMB Charter). Life-threatening events and deaths will be reported to the DSMB immediately. In addition the DSMB will be notified of unexpected significant new safety data on an ad hoc basis as deemed necessary by the Project Director and the ADCS.

14. SAMPLE SIZE AND STATISTICAL METHODS

14.1. Overview of the statistical design

The study will implement a seamless phase 2a-2b sequential design with a go/no-go futility analysis occurring after one year of follow-up. While the primary efficacy endpoint for the first phase of the study is p-tau₂₃₁, the futility analysis occurring at the end of phase 2a will be based upon change in p-tau₂₃₁ or p-tau₁₈₁. Regardless of the decision to continue onto phase 2b, unadjusted inference for the change in p-tau₂₃₁ comparing treatment to control will be reported at the end of phase 2a. In the event that the trial does continue on to phase 2b, final inference will be adjusted for the futility analysis based on p-tau₂₃₁ and p-tau₁₈₁.

14.2. Analysis of the primary outcome

The primary analysis of phase 2a will focus on the change in p-tau₂₃₁. The primary analysis will be based on the Intention-to-Treat population, defined as all participants who were randomized to study drug or treatment. We will model the change in p-tau₂₃₁, using an analysis of covariance model (ANCOVA). That is, 48-week p-tau₂₃₁ will be regressed upon baseline p-tau₂₃₁ and an indicator for treatment vs. placebo. The Huber-White robust variance estimator will be used to estimate the variance of the estimated difference in the mean change in p-tau₂₃₁ comparing treatment to placebo. Along with the estimated difference in mean change in p-tau₂₃₁, a Wald-based 95% confidence interval and corresponding p-value will be computed and presented.

14.3. Implementation of the futility boundary

At the conclusion of phase 2a, a futility decision of whether to continue follow-up of patients for an additional year will be based upon either the change in p-tau₂₃₁ or p-tau₁₈₁ after 48-weeks. The decision boundary for continuing to an additional 48-weeks of follow-up will be based upon the observed mean differences in p-tau₂₃₁ or p-tau₁₈₁ after 48-weeks of treatment. Specifically, the trial will continue to the second phase if the observed relative reduction in change in p-tau₂₃₁ or p-tau₁₈₁ is greater than 0.5 pg/ml, corresponding to a 10% reduction based upon an anticipated change of 5.1 pg/ml in the control arm (a similar distribution is expected for the change in or p-tau₂₃₁ and p-tau₁₈₁).⁴⁴ Individually, this boundary decision corresponds to a Pocock futility boundary at 50% of the maximal statistical information, maintaining level 0.025 for a one-sided hypothesis test.^{55, 56} While implementation of the futility boundary will not affect inference for the primary outcome in phase 2a, it will need to be accounted for in the inference corresponding to the outcomes of phase 2b. In the event that the trial does proceed to phase 2b, final inference will account for the futility decision by utilizing a Benjamini-Hochberg adjustment⁵⁷ for multiplicity bias stemming from the use of two biomarkers in the decision to continue the trial. In this case, simulation will be used to adjust the final inference at phase 2b in order to maintain an overall familywise type I error rate of .05.

14.4. Statistical power for phase 2a.

Based upon prior reported data, it is expected that the change in p-tau₂₃₁ over one year will be approximately 5.1 pg/ml with a standard deviation of 1.5.⁴⁴ With a sample size of 48 participants, a 1:1 randomization scheme, and a 10% per year loss-to-follow-up rate, the proposed study will attain approximately 80% power for detecting a true absolute difference in mean within-subject change in p-tau₂₃₁ of 1.26 pg/ml (24.5% relative reduction). Further, the probability of successfully passing the “go/no-go” decision for a second year of clinical follow-up is 80% if the true absolute difference in the within subject change in either CSF p-tau₂₃₁ or p-tau₁₈₁ 1.06 pg/ml (20.9% relative reduction).

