- End of study: At 48-weeks, participants will complete all study assessments. Participants will be provided additional study drug (6-months supply) for the period of time for go/no-go analysis.
- Early termination: In the event of early termination due participant withdrawal of consent or removal by the investigator from the trial, the 48-weeks/early termination visit should be completed in all possible cases, if the participant has been randomized to therapy or placebo. No new investigational product will be administered.
- Unscheduled visits: If needed, unscheduled visits can be performed at the discretion of the Site Principal Investigator. Unscheduled visits should include collection of adverse events, concomitant medications, brief neurological and physical examination, and clinical blood laboratories, if indicated.
- Go/no-go: At the completion of the go/no-go analyses, participants will complete an additional visit to assess safety and collect study medication (no-go) or to be enrolled in the 48-weeks extension study (go). In the event of a “go” decision, trial duration will be extended to 96-weeks. Participants will remain blinded to randomization and group assignment will be unchanged. A safety visit will be performed at 74-weeks. The end of study visit will be performed at 96-weeks, and will include the co-primary outcome measures of the ADAS-cog13 and the ADCS-ADL-MCI, as well as the CDR-SB, neurological and physical exams, blood laboratories, assessment of adverse events, MRI, and lumbar puncture for CSF protein analysis.

9.2.2. Safety assessments. Participants will undergo brief physical and neurological examinations, laboratory testing, and EKG at all follow-up visits (12, 24, and 48-weeks /early termination). Adverse events will be assessed by the study site clinician. Adverse events include signs or symptoms that may or may not be related to study medication, abnormalities detected during physical examination, or clinically significant laboratory abnormalities. The Columbia Suicidality Severity Rating Scale (C-SSRS) will be performed at the baseline, 24-week, and 48-week visits. Adverse events will be graded as mild, moderate, or severe according to section 13.1.1, and recorded on case report forms. Regular safety reports will be prepared by the ADCS and submitted to an independent Data and Safety Monitoring Board (see section 13.3.3).

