12.2. Secondary outcomes measures

12.2.1. CSF analyses

1. CSF p-tau₁₈₁. CSF p-tau₁₈₁ is a well-replicated biomarker for AD and is used frequently in large AD natural history studies and clinical trials.^{34, 44}
2. CSF total tau. Increased total tau in the CSF is believed to be a marker of neuronal injury or degeneration, though this change is not necessarily unique to AD. Total tau may increase by 1.5-2 fold in AD, suggesting that treatment-related reduction in total tau would be strongly indicative of a disease modifying effect.³⁴

3. CSF A β ₄₂. Reduced CSF A β ₄₂ is strongly associated with AD.³⁴ Although preclinical work at our institution did not find an effect of nicotinamide treatment on brain A β ₄₂ levels, work from another laboratory, in which experiments involved longer exposure to nicotinamide did see treatment-induced amelioration of A β burden.²
4. CSF A β ₄₀. We will also examine CSF levels of the shorter (40 amino acid) peptide fragment of A β .

CSF biomarker and APOE genotype analyses. Analyses of p-tau₂₃₁ levels will be performed by Quanterix (www.quanterix.com). Quanterix uses proprietary technology, called the Accelerator, and their Simoa Discovery kits to assay p-tau₂₃₁ levels. Preliminary analyses reveal low variability among control samples, adequate differential between cases and controls, and strong correlation between this assay and p-tau₁₈₁ (unpublished results), justifying selection of this assay.

The ADCS Biomarker Core will perform the remaining CSF protein analyses. Validated assay platforms from Meso Scale Discovery (Rockville, MD) will be used to assess total tau, A β ₄₂ and A β ₄₀ levels. Fujirebio INNOTEST® protein assay kits will be used to assess p-tau₁₈₁ levels.

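### The 80% go probability at 1.06 pg/ml in Protocol 14.4 does not follow from the protocol's inputs, which give about 89% for one marker and reach 80% at about 0.88 pg/ml

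*Protocol*

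**What the plan says.** Protocol 14.3 sets the go rule. The trial continues if the observed reduction in p-tau231 or p-tau181, treatment against control, "is greater than 0.5 pg/ml, corresponding to a 10% reduction based upon an anticipated change of 5.1 pg/ml in the control arm". The same section says that "this boundary decision corresponds to a Pocock futility boundary at 50% of the maximal statistical information", at one-sided level 0.025, and that a similar distribution is expected for both markers.

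On timing, 14.3 reads "At the conclusion of phase 2a, a futility decision of whether to continue follow-up of patients for an additional year", and 14.1 describes a "go/no-go futility analysis occurring after one year of follow-up".

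Protocol 14.4 assumes a one-year change of 5.1 pg/ml with SD 1.5, 48 participants at 1:1 and 10% loss per year. It draws two figures from these:

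- Power for p-tau231, quoted for 1.26 pg/ml: "the proposed study will attain approximately 80% power for detecting a true absolute difference in mean within-subject change in".
- Chance of a go, quoted for 1.06 pg/ml in p-tau231 or p-tau181 and given as a 20.9% relative reduction: "decision for a second year of clinical follow-up is 80% if the true absolute difference in the within subject change in either CSF".

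SAP 1.3 repeats the first figure but not the second.

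**The concern.** Both figures in 14.4 describe the same estimate: the between-arm difference in 48-week change. They should therefore share one standard error. The go threshold is a fixed 0.5 pg/ml, so the go probability follows directly from that standard error, and the printed 80% looked too low.

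The figure matters because it is the only go probability the protocol gives for the rule that decides whether all participants continue for a second year. A reader would take from it a 20% chance of a wrong no-go at 1.06 pg/ml, and would believe that a true difference of 1.06 pg/ml is needed for an 80% chance of continuing. There is also a downstream use. Section 14.3 says simulation will adjust phase 2b inference for the futility decision, and that simulation needs the information available at the go look.

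**Working it through.** **Inputs.** SD of change 1.5, 48 participants at 1:1 and 10% loss (Protocol 14.4, SAP 1.3); boundary 0.5 pg/ml and control change 5.1 pg/ml (Protocol 14.3). Evaluable per arm: 24 × 0.9 = 21.6. Normal approximation throughout.

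**Standard error of the difference.** SE = 1.5 × √(2/21.6) = 0.456.

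**Step 1: the power figure reproduces.** Power at 1.26 = Φ(1.26/0.456 − 1.96) = 78.8%. With 22 per arm it is 79.6%. This matches the stated 80% or so and confirms the inputs.

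**Step 2: the go figure does not.** P(go | 1.06) = Φ((1.06 − 0.5)/0.456) = 89.0%. A wrong no-go is therefore 11.0%, not 20%. The difference that gives 80% is 0.5 + 0.8416 × 0.456 = 0.884 pg/ml, and 0.884/5.1 = 17.3%.

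**Step 3: sensitivity to sample size and boundary.**

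| Per arm | Boundary | P(go at 1.06) | Difference for 80% (pg/ml) |
|---|---|---|---|
| 24 (no loss) | 0.50 | 90.2% | 0.864 |
| 22 | 0.50 | 89.2% | 0.881 |
| 21.6 | 0.50 | 89.0% | 0.884 |
| 21 | 0.50 | 88.7% | 0.890 |
| 19.44 (two years' loss) | 0.50 | 87.8% | 0.905 |
| 21.6 | 0.51 | 88.6% | 0.894 |

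If 1.5 is the SD of change, adjusting for baseline in the ANCOVA could only raise these probabilities.

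**Step 4: the either-marker rule.** The documents give no correlation between the two estimated differences, so a range is assumed, with SD 1.5 for both markers.

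| Correlation | Go, one marker at 1.06 and the other null | Go, both at 1.06 | Go, no effect on either |
|---|---|---|---|
| 0 | 90.5% | 98.8% | 25.5% |
| 0.5 | 89.2% | 96.3% | 22.3% |
| 0.9 | 89.0% | 92.3% | 17.6% |
| 0.99 | 89.0% | 90.1% | 14.9% |

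For one marker under no effect, Φ(−0.5/0.456) = 13.7%. The second marker only moves the result further from 80%.

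**Step 5: what 80% at 1.06 would require.** SE = 0.56/0.8416 = 0.665. That means SD 2.19 at 21.6 per arm, or 2 × 1.5²/0.665² ≈ 10 per arm at SD 1.5. With that SE, power at 1.26 would be Φ(1.26/0.665 − 1.96) = 47%, which contradicts the sentence before it.

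**Step 6: probable source.** Halving the information gives SE = √2 × 0.456 = 0.645 and P(go | 1.06) = Φ(0.56/0.645) = 80.7%, close to the printed 80%. With 10 per arm, the 80% point is 1.065 pg/ml (20.9%, the printed percentage). It appears that the 50% information fraction in 14.3 was applied to the evaluable sample. This is an inference; the protocol does not say so. The same SE would give 50% power at 1.26 and a 21.9% chance of a go under no effect for one marker.

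**The case against.** The strongest reply is that the list of inputs above leaves one out. Section 14.3 places the boundary at 50% of maximal information, and a half-information look nearly reproduces the printed figure. On this view 14.4 agrees with one clause of 14.3 and conflicts with another, so the fault is an undefined information fraction, not arithmetic.

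The threshold itself lends this some support. Take a futility-only Pocock-type boundary at half information with one-sided level 0.025, and type II errors of 0.025, 0.10 and 0.20 (assumed, since the documents give none). If 0.456 is the SE at maximal information, the boundary is 0.46, 0.57 or 0.64 pg/ml, a range that contains 0.5. If 0.456 is the SE at the look itself, the boundary is 0.33, 0.40 or 0.45 pg/ml, which falls short of 0.5.

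This stands as an account of where the numbers may have come from, and as a reason to ask what maximal information means. It does not rescue the 80%. Sections 14.1 and 14.3 put the decision after one year, at the end of phase 2a, and no section describes a look at half the participants. However 0.5 was derived, applying it to all 48-week data gives 89%. Nor does counting later data help: 9.2.1 plans, after a go, "assessment of adverse events, MRI, and lumbar puncture for CSF protein analysis" at 96 weeks, but this leaves the SE at 48 weeks unchanged, and the phase 2b co-primaries are ADAS-cog13 and ADCS-ADL.

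Two further points are fair. The error is conservative, and it changes no participant's actual chance of continuing. The no-effect probabilities are an addition that the protocol never promised, and they rest on an assumed correlation. Section 12.2.1 reports "adequate differential between cases and controls, and strong correlation between this assay and" p-tau181, which makes the higher correlations more plausible, but that concerns assay readings rather than between-arm differences in change.

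**Conclusion.** The stated 80% go probability at 1.06 pg/ml is wrong for the rule as the protocol describes its execution. For one responding marker it is 89.0% (88.7% to 90.2% for 21 to 24 per arm), and 80% is reached at about 0.88 pg/ml (17.3%) rather than 1.06 pg/ml (20.9%). This rests on SD 1.5, a normal approximation and a look using all available 48-week CSF. Considering one marker alone is the reading most favourable to the printed figure.

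The error is confined to a descriptive statement. The rule can still be applied as written, and the sample size, the 1.26 pg/ml power statement and phase 2a inference are unaffected. It should be fixed because it misstates a key property of the go/no-go rule and leaves the information at the look ambiguous. Compared with the apparent half-information figures, the corrected ones are better in both directions: 89% against 81% at 1.06 pg/ml, and 13.7% against 21.9% under no effect for one marker.

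**What to change.** Keep the 0.5 pg/ml rule and make three wording changes:

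1. **Protocol 14.4, go probability.** State that with 48 participants, 10% loss and SD 1.5, a single responding marker passes with probability about 89% at a true difference of 1.06 pg/ml and 80% at about 0.88 pg/ml (17%).
2. **Protocol 14.4, no effect.** Add the go probability under no effect: about 14% for one marker and about 15% to 25% for either marker, with the assumed correlation stated.
3. **Protocol 14.3, information fraction.** Reconcile the 50% information wording with a look that uses all available 48-week CSF. Either define maximal information, including whether the 96-week CSF counts, or describe 0.5 pg/ml as a fixed threshold. If a half-information look was intended, say what it refers to and derive both the threshold and the go probability from it.

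The cost is text in Protocol 14.3 and 14.4. The rule, sample size, primary analysis and SAP do not change.

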14.5. Handling of missing data

In primary analyses, outcome values will not be imputed. Further sensitivity analyses for the impact of potential missing data will be conducted following study completion. These will include a multiple imputation analysis and a pattern mixture model analysis considering various departures from the estimated treatment effect using completely observed data.⁵⁸

15. ETHICS

15.1. Ethical Conduct of Study

This study will be conducted according to Good Clinical Practice, the Declaration of Helsinki,⁵⁹ the Belmont Report, and US 21 CFR Part 50 – Protection of Human Subjects – and Part 56 – Institutional Review Boards.

15.2. Institutional Review Board (IRB)

All materials will be submitted, reviewed, and approved by the UC Irvine Institutional Review Board. UCLA will utilize the reliance agreement available through the UC BRAID/UC Reliance Services mechanism to achieve approval for this multisite trial using a single IRB mechanism.

15.3. Human subject protection

The substantial clinical experience with nicotinamide in a variety of therapeutic areas, including doses higher than that proposed in this study, suggest that the overall risk for this study is low. We will nevertheless utilize the ADCS DSMB to ensure that the study has appropriate monitoring for safety. The DSMB will be notified immediately of any life-threatening events or deaths. The DSMB will receive blinded reports of adverse events and serious adverse events on a quarterly basis and will be convened telephonically for the purpose of assessing trial continuation. At any time, the DSMB will be able to request additional data, including unblinded data, for the purpose of safety review. The DSMB may recommend halting of the study prior to conclusion or modification to the protocol at any time.

15.4. Informed Consent Document

The principles of informed consent in the current edition of the Declaration of Helsinki will be implemented before any protocol-specified procedures are carried out. Informed consent will be obtained in accordance with US 21 CFR 50.25 and requires approval from the UCI IRB. Consent forms must be in

a language fully comprehensible to the prospective participant and the dated signature of the participant will document consent.

Informed consent will be performed in the private research setting by the site PI or study coordinator. The capacity to provide informed consent will be assessed using the University of California Post-Consent Assessment Instrument. Individuals lacking the capacity to provide informed consent may be enrolled provided that 1) a legally authorized representative (LAR) is able to give surrogate consent, and 2) the participant provides assent. The LAR must be certified as appropriate using the “Self-Certification of Surrogate Decision Makers for Potential Subject’s Participation in University of California Research.”

Each participant must have a qualified study partner (see section 10.1.1) and this individual must also provide written informed consent to participate.

15.4. Participant Confidentiality

All participants have a right to protection against invasion of privacy. After completion of the informed consent process, participants will be assigned a study identification number. Throughout this study, data will be identified in the Case Report Forms by the subject identification number only.

16. DATA HANDLING AND RECORDING

16.1. Data collection and management responsibilities

Case report forms (CRFs) will be provided for use as source documents and used for primary data collection at the sites. These will be maintained for each participant enrolled in the study. The investigator is responsible for ensuring the accuracy, completeness, legibility, and timeliness of the data reported. All source documents must be completed in a neat, legible manner to ensure accurate interpretation of data. Black ink is required. When making changes or corrections, cross out the original entry with a single line, and initial and date the change.

Participant visit data will be entered into the ADCS Electronic Data Capture (EDC) system within 72 hours of visit completion. EDC entry will include manual entering of data and the scanning and uploading of some specific CRFs (see procedures manual). Data reported in the eCRF derived from source documents should be consistent with the source documents or the discrepancies should be explained and captured in a progress note and maintained in the participant’s official electronic study record. Clinical data (including AEs, concomitant medications, and adverse reactions data) and clinical laboratory data will be entered into the EDC. The data system includes password protection and internal quality checks, such as automatic range checks, to identify data that appear inconsistent, incomplete, or inaccurate. Clinical data will be entered directly from the source documents.

